## 8.2 SAFETY ASSESSMENTS

There will be no direct contact between participants and study staff, as consent and assessment procedures are completed digitally. Individuals who are deemed ineligible due to elevated depressive symptoms are presented with mental health resources and crisis contacts when exiting the survey platform. Likewise, individuals indicating recent thoughts of suicide are presented with resources and crisis contact information and are informed that study staff do not review their responses.

## 8.3 ADVERSE EVENTS AND SERIOUS ADVERSE EVENTS

### 8.3.1 DEFINITION OF ADVERSE EVENTS

An adverse event is any experience or abnormal finding that has taken place during a research project and was harmful to the subject participating in the research, or increased the risks of harm in the research, or had an unfavorable impact on the risk/benefit ratio.

For this study, expected AE include worsening depressive symptoms and onset of suicidal ideation.

### 8.3.2 DEFINITION OF SERIOUS ADVERSE EVENTS

Serious adverse event (SAE) is an adverse event that: results in death; is life-threatening (places the participant at immediate risk of death from the event as it occurred); results in inpatient hospitalization or prolongation of existing hospitalization; results in a persistent or significant disability/incapacity; results in a congenital anomaly/birth defect; or based upon appropriate medical judgment, may jeopardize the subject's health and may require medical or surgical intervention to prevent one of the other outcomes listed in this definition.

### 8.3.3 CLASSIFICATION OF AN ADVERSE EVENT

#### 8.3.3.1 SEVERITY OF EVENT

For adverse events (AEs) not included in the protocol defined grading system, the following guidelines will be used to describe severity.

- **Mild** – Events require minimal or no treatment and do not interfere with the participant's daily activities.
- **Moderate** – Events result in a low level of inconvenience or concern with the therapeutic measures. Moderate events may cause some interference with functioning.
- **Severe** – Events interrupt a participant's usual daily activity and may require systemic drug therapy or other treatment. Severe events are usually potentially life-threatening or incapacitating. Of note, the term "severe" does not necessarily equate to "serious".]

#### 8.3.3.2 RELATIONSHIP TO STUDY INTERVENTION/EXPERIMENTAL MANIPULATION

All adverse events (AEs) will have their relationship to study procedures, including the intervention, assessed by an appropriately trained clinician based on temporal relationship and his/her clinical judgment. [name] will be responsible for reporting adverse events and serious adverse events. The degree of certainty about causality will be graded using the categories below.

- **Definitely Related** – There is clear evidence to suggest a causal relationship, and other possible contributing factors can be ruled out. The clinical event, including an abnormal laboratory test result, occurs in a plausible time relationship to study procedures administration and cannot be explained by concurrent disease or other drugs or chemicals. The response to withdrawal of the study procedures should be clinically plausible. The event must be pharmacologically or phenomenologically definitive.
- **Probably Related** – There is evidence to suggest a causal relationship, and the influence of other factors is unlikely. The clinical event, including an abnormal laboratory test result, occurs within a

reasonable time after administration of the study procedures, is unlikely to be attributed to concurrent disease or other drugs or chemicals, and follows a clinically reasonable response on withdrawal.

- **Potentially Related** – There is some evidence to suggest a causal relationship (e.g., the event occurred within a reasonable time after administration of study procedures). However, other factors may have contributed to the event (e.g., the participant's clinical condition, other concomitant events). Although an AE may rate only as "possibly related" soon after discovery, it can be flagged as requiring more information and later be upgraded to "probably related" or "definitely related", as appropriate.
- **Unlikely to be related** – A clinical event, including an abnormal laboratory test result, whose temporal relationship to study procedures administration makes a causal relationship improbable (e.g., the event did not occur within a reasonable time after administration of the study procedures) and in which other drugs or chemicals or underlying disease provides plausible explanations (e.g., the participant's clinical condition, other concomitant treatments).
- **Not Related** – The AE is completely independent of study procedures administration, and/or evidence exists that the event is definitely related to another etiology. There must be an alternative, definitive etiology documented by the clinician.]

### 8.3.3.3 EXPECTEDNESS

[name] will be responsible for determining whether an adverse event is expected or unexpected. An AE will be considered unexpected if the nature, severity, or frequency of the event is not consistent with the risk information previously described for the study procedures.

### 8.3.4 TIME PERIOD AND FREQUENCY FOR EVENT ASSESSMENT AND FOLLOW-UP

The occurrence of an adverse event (AE) or serious adverse event (SAE) may come to the attention of study personnel during review of assessments of a study participant or if a participant makes direct contact with study staff through the project e-mail address. All AEs, not otherwise precluded per the protocol, will be captured on the appropriate case report form (CRF). Information to be collected includes event description, time of onset, assessment of severity, relationship to study procedures, and time of resolution/stabilization of the event. All AEs occurring while on study will be documented appropriately regardless of relationship. Within 48 business hours of learning of these events, the coordinator will then bring all possible AEs to the attention of the PI for evaluation and appropriate reporting. AE's will be assessed by the PI for expectedness (expected, unexpected) and relatedness (definitely related, probably related possibly related, unlikely related, not related). A log of all AE's will be maintained by the study coordinator, and the log will be additionally reviewed for completeness at weekly intervals during the active recruitment period.

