### 1.2 SCHEMA

### 1.3 SCHEDULE OF ACTIVITIES

	Screening	Baseline Survey	Weekly (Every Sunday for 5 weeks)	Daily (42 days; Intervention-only)	6-week follow-up (6 th Sunday)
Informed Consent	X				
Demographics	X				
Primary Randomization (Survey Only)		X			
Secondary Randomization (MRT)		X			
Outcome Evaluations					
Flourishing Scale	X		X	*	X
Depression (PHQ-9) and Anxiety (GAD-7)	X		X		X
Coping Self-Efficacy	X		*		X
UCLA-Loneliness Scale	X		X		X
Mental Health Service Utilization	X				X
Pittsburgh Sleep Quality Index-Adapted		X	*		X
Physical Activity (YRBS Adaptation)		X	*		X
Interpersonal Needs Questionnaire (INQ)		X			X
DERS-Emotional Awareness		X	X	*	X
Brief COPE		X			X
National Comorbidity Survey (Suicidal Ideation and Behavior)		X	*		*
Perceived Stress Scale		X	*	*	X
Life Events Checklist (LEC-5)		X			
Readiness for Help-Seeking		X	*		X
Daily Mood				*	
Feasibility/Acceptability Survey					X
Adverse Events Reporting		X			X
Note: X = Full-scale; * = Abbreviated version					

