#### Managing Distress and Safety Concerns

Our team has extensive experience conducting longitudinal research studies with individuals at risk for depression and suicide. [name] will closely supervise research staff to ensure potential safety issues are appropriately addressed in accordance with the protocol. All participants are free to terminate the study at any time or refuse to respond to any questionnaire item. Any suicidal ideation endorsement on the baseline, weekly, or follow-up survey will result in an automated notification informing participants about crisis resources (phone numbers and text line) and recommending use of these resources if they feel unable to resist acting on their suicidal thoughts. Participants will be informed that their survey responses are not monitored by research staff.

Finally, in the event that a participant sends a text message to the phone number used to send daily surveys or supportive text messages, the participants will receive an automated response with information that the phone number does not receive text messages or phone calls and with information about how to contact the study with questions during business hours as well as information for accessing emergency services/immediate support (e.g., crisis line, local emergency department).

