*Sleep (Baseline/Weekly-abbv./Follow-up).* We will use a 9-item adapted version of the Pittsburgh Sleep Quality Index (Buysse et al., 1989) to capture self-report of sleep duration, quality, and sleeping difficulties at baseline and follow-up. Two items focused on sleep duration and quality will be utilized at weekly assessments.

*Physical activity (Baseline/Weekly/Follow-up).* We use three derived from the Youth Behavior Risk Survey (Grunbaum et al., 2002) to assess frequency and duration of moderate and vigorous exercise at baseline, weekly, and follow-up assessments.

*Interpersonal functioning (Baseline/Follow-up).* We use 15 items from the Interpersonal Needs Questionnaire (Van Orden et al., 2012), a self-report measure of perceived burdensomeness and thwarted belongingness-- two interpersonal constructs believed to contribute to suicidal desire.

*Emotional Awareness (Baseline/Weekly/Follow-up).* We use the 6-item subscale 'Emotional Awareness' from the Difficulties in Emotion Regulation Scale (Gratz & Roemer, 2004) at baseline, weekly, and follow-up assessments.

*Coping Behaviors (Baseline/Follow-up).* We use the 28-item Brief Cope (Carver, 1997) to assess frequency of using 14 specific coping behaviors that encompass various forms of problem-focused coping, emotion-focused coping, and avoidant coping strategies.

*Suicidal thoughts and behaviors (Baseline/Weekly—abbv./Follow-up—abbv.).* 4 items adapted from the National comorbidity survey will assess history of suicidal thoughts and behaviors at baseline, and two items will assess past-week suicidal thoughts at weekly and follow-up assessments.

*Readiness for help-seeking (Baseline/Weekly-abbv./Follow-up).* We use four items on a 10-point readiness scale (King et al., 2022) for seeking help from different sources (e.g., family/friends, online resources, professional services, support group) for mental health at baseline and follow-up. Weekly assessments will include two items: readiness for online resources and professional services.

*Intervention Acceptability (Follow-up).* We use a modified version of the 4-item Acceptability of Intervention Measure (Weiner et al., 2017) to obtain self-report subjective ratings of intervention acceptability and participants will indicate acceptability of numerous intervention features (e.g., frequency/timing of surveys, personalized feedback; confidentiality; satisfaction; helpfulness) using a 7-point agreement scale (strongly disagree to strongly agree).

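### The adverse event log alone may under-count the two expected harms, which both arms report on weekly but no safety analysis tabulates

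*Combined protocol and SAP*

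**What the plan says.** - **Routes to the log.** Section 8.3.4 says an adverse event "may come to the attention of study personnel during review of assessments of a study participant", or may become known when a participant writes to the project e-mail address. It adds: "All AEs occurring while on study will be documented appropriately regardless of relationship".
- **Notices to participants.** Section 2.3.3: "Participants will be informed that their survey responses are not monitored by research staff". Section 8.2, on those who report recent suicidal thoughts: they "are informed that study staff do not review their responses".
- **Expected events.** Section 8.3.1: "For this study, expected AE include worsening depressive symptoms and onset of suicidal ideation".
- **Where these are measured.** Section 8.1 places the PHQ-9 at screening, weekly and at follow-up, and states that "two items will assess past-week suicidal thoughts at weekly and follow-up assessments". Section 6.1.1 gives the weekly survey to both arms.
- **Scheduled reporting.** In the section 1.3 table, the row "Adverse Events Reporting" is marked at the baseline survey and the 6-week follow-up only.
- **Log check.** Section 8.3.4: "the log will be additionally reviewed for completeness at weekly intervals during the active recruitment period". Section 5.5 puts recruitment at about 10 days; section 5.4 gives two weeks for screening.
- **Analysis.** Section 9.4.4, Safety Analyses, is marked N/A.

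**The concern.** The protocol names two harms it expects and measures both every week in everyone. It does not say how a weekly answer becomes an entry in the log. One stated route depends on staff reviewing assessments, while participants are told that staff do not. The other route depends on the participant writing in. Worsening or new ideation disclosed only in a weekly survey could stay out of the log.

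The log, or something built from it, presumably feeds the yearly adverse event summary to the IRB (section 8.3.5). Frequency also matters elsewhere. Section 8.3.3.3 treats an event as unexpected if its frequency departs from the described risk, and section 8.4.1 uses frequency in defining an unanticipated problem. Section 3 compares depressive symptoms between weeks with and without an intervention component. That comparison does not show how many participants got worse, and no analysis is named for the suicidal-thought items collected after baseline.

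**Working it through.** The plan states no adverse event rate, threshold or safety precision, so there is no figure to reproduce. The check sets the texts side by side, dates the log check, and finds the precision of the proposed table.

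**1. Do the texts agree?** The notice in 2.3.3 can be read as no live monitoring. The one in 8.2 is harder to square with review of assessments in 8.3.4. Other clauses presuppose that some answers are seen. Section 2.3.1 keeps the identity link partly so the team can act on signs of imminent risk. Section 7.2 allows discontinuation for a newly developed exclusion criterion, and a PHQ-9 above 14 is one (section 5.2). No section available for this review says who reviews which answers, how often, or what change counts as an event.

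**2. When does the log check stop?** Section 8.1 launches the screening survey on a Tuesday; call it day 0.
- Sundays fall on days 5, 12, 19 and so on.
- Recruitment ends at about day 10 (section 5.5) or day 14 (section 5.4), giving 10/7 = 1.4 or 14/7 = 2 weekly checks.
- A participant's sixth Sunday is at the earliest day 5 + 5 × 7 = 40. For someone enrolled after the first Sunday it is day 12 + 35 = 47 or later.
- Read literally, the check stops at least 40 − 14 = 26 days before the earliest possible final follow-up.

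**3. What could the week-6 report recover?** The row in section 1.3 has no arm restriction, so it covers both arms among those who complete follow-up. Its content and recall period are not shown. The follow-up suicidal-thought items cover the past week only, so they do not themselves recover ideation from earlier weeks.

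**4. Why the captured share matters (illustration).** Let s be the share of affected participants whose event reaches the log. With no logged event in 120 participants, the exact two-sided 95% upper limit on the true proportion is (1 − 0.025^(1/120)) / s = 3.0% / s. For assumed s of 1, 0.5, 0.25 and 0.1 this gives 3.0%, 6.1%, 12.1% and 30.3%. The documents do not fix s; these values are assumptions, not estimates.

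**5. Precision of a by-arm table.** The same limit for zero events, with every participant contributing data, is:
- assessment-only: 1 − 0.025^(1/30) = 11.6%
- intervention: 1 − 0.025^(1/90) = 4.0%

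**The case against.** The strongest reply is that the texts can be reconciled. The notice in 2.3.3 directly follows the automated crisis message and plausibly warns students not to expect a staff response. Section 8.3.4 says only that events may come to attention, and later review of stored answers is compatible with no live monitoring. The duty to bring possible events to the investigator within 48 business hours has no recruitment-period limit. This is a pilot described as minimal risk with descriptive aims.

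Much of this stands, and it rules out two stronger readings that a reader might infer.

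- *That nobody looks at the answers, so a low count means nothing.* The notices address participants and are not staff instructions. Adverse event reporting is also scheduled at week 6 in both arms.
- *That survey counts measure the loss.* Of 120 × 6 = 720 planned weekly and follow-up surveys, 120 × 5 = 600 fall in weeks without scheduled adverse event reporting. At least 120 × 4 = 480 (10-day window) or 120 × 3 = 360 (14-day window) of those 600 come after the log check ends. Neither figure counts missed events: the week-6 report may look back over the whole period, and the check concerns the log, not survey answers.

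The reply does not explain why a completeness check should stop when recruitment does, or why harms named in advance and measured weekly should go untabulated.

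**Conclusion.** The concern holds in a limited form. As written, the log alone may under-count worsening depression and onset of suicidal ideation, and the plan has no safety table to set beside it. The size of any under-count is unknown, because the documents give neither an event rate nor a captured share.

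Severity is minor. Sections 2.3.3 and 10.1.6 provide automatic crisis information, so this concerns counting and consistency, not absent protection. Mild and moderate expected events are not individually reported to the IRB (section 8.3.5), and none of the feasibility measures in section 9.4.2 uses the log.

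The conclusion rests on the protocol text and on taking the recruitment-period limit literally. The consent form, case report form, Risk Management Protocol, Manual of Procedures and section 10.1.5 (key roles) were not available for this review and may settle how answers reach the log.

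**What to change.** 1. **Section 8.3.4:** run the weekly log check until the last 6-week follow-up. On the dates above this adds roughly four to six checks.
2. **Section 9.4.4:** replace N/A with a descriptive table by arm (90 and 30) from the stored weekly and follow-up surveys, showing:
   - participants with past-week suicidal thoughts, split by ideation at entry, because such ideation is not an exclusion and the named event is onset;
   - participants whose PHQ-9 goes above 14, since all enter at 5 to 14, with the distribution of the largest PHQ-9 rise from screening, so that a move from 14 to 15 can be told from a large rise;
   - surveys completed per arm, as the denominator.

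   Give 95% intervals and no between-arm test.
3. **Sections 2.3.3, 8.2 and 8.3.4 (wording):** make them agree, for example by saying that responses are not monitored in real time, if that is the intent. Do not resolve the conflict by deleting review of assessments, which would remove a capture route.

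The cost is a few sentences, a longer run of an existing check and one table from data already collected. The table will be imprecise, more so if surveys are missed, and should be presented as description only.

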## 4 STUDY DESIGN

### 4.1 OVERALL DESIGN

This project is a two-armed randomized control trial (RCT) with an embedded MRT aimed to help develop a mobile health intervention for college students at-risk for depressive episodes. Participants will complete daily and weekly assessments, be randomized to receive weekly PF reports regarding mood and stress and be randomized to receive text-messages containing tips/strategies related to self-care, time management, and interpersonal connection/support. We will utilize follow-up surveys and objective indicators of engagement/participation to assess feasibility and acceptability of the intervention. Proposed mechanisms of change (e.g., coping efficacy, perceived stress, readiness for help-seeking) will be assessed by exploring associations of intervention components (i.e., text messages, PF reports) with relevant outcomes. This study has the following aims: 1) demonstrate feasibility and acceptability in intervention components, and 2) examine the initial impact of the mobile health intervention on proposed mechanisms of change. The total time for study completion for an individual participant is 6 weeks, with completion marked as completing the 6-week follow-up survey. The entirety of the study will run for 6 months.

We will send out a brief mental health screening survey to 2,500 first-year college students, and anticipate that 425 will consent to participate and complete the screen, and 142 will meet study inclusion criteria for mild-to-moderate depressive symptoms and no current mental health treatment. From this group, we anticipate 120 will provide their cellphone number, complete the baseline survey (~15 additional minutes to 8-minute screening survey), and be randomized into the six-week intervention trial (90 into the 'Pilot MRT' intervention condition, and 30 into the 'Assessment Only'

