#### 5.4 SCREEN FAILURES

Screen failures are defined as participants who consent to participate in this study but are not subsequently assigned to the study intervention or entered in the study. Individuals who do not meet the criteria for participation in this trial (screen failure) because of meeting one or more exclusion

criteria will not be re-screened, as the initial screening period for this intervention will occur over the course of only two weeks.

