## 5.5 STRATEGIES FOR RECRUITMENT AND RETENTION

We will send out an e-mail to a randomized batch of approximately 2,500 students (2,000 UM-Ann Arbor, 500 UM-Flint), provided by the respective student registries, inviting them to complete an initial 8-minute survey. We anticipate approximately 425 (17%) will consent to participate and complete the **screening** survey, and that 142 (33%) will screen as eligible (mild-to-moderate depression symptoms as defined by PHQ-9 score of 5-14; no current MH treatment) for the intervention portion of the study. The screening survey will be administered to all invited participants and takes approximately 8-10 minutes to complete. After initially sending out the screening survey, we will also send two follow-up reminders via email a couple days apart to remind potential participants of the opportunity to participate in the study. Our full sample will be recruited in this ~10-day period.

We anticipate 120 students (85%) will continue to this next phase of the study, provide a cell-phone number, and complete the **baseline** survey (all within this same Qualtrics flow as the screening survey). Once the baseline survey has been completed, participants will be randomized 3:1 to a “Assessment Only” (n = 30) or “Intervention” (n=90) condition. Based on student enrollment and screening rates from a prior study, we anticipate our sample to be 67% female, 63% White, 20% Asian, 9% Black, 8% Multi-racial, and 12% Hispanic.

Our research group has developed several successful strategies to improve participant retention. For completion of the baseline survey, daily and weekly assessment surveys, and final follow-up survey we will provide participants with financial compensation in the form of a re-loadable digital Visa card. For the initial completion of the screening survey, participants will be entered into a drawing for one of ten \$50 digital Visa cards. For completion of the baseline survey, participants will receive \$20. For daily surveys, participants will receive \$1 for each completed survey. For weekly assessments, participants will receive \$10 for each completed survey. Finally, participants will receive \$25 for completing the final, 6-week follow-up survey. Participants will have payments issued each week based on the number of completed surveys.

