### 8 STUDY ASSESSMENTS AND PROCEDURES

## 8.1 ENDPOINT AND OTHER NON-SAFETY ASSESSMENTS

To recruit participants, we will obtain e-mail addresses of 2,500 first-year undergraduate students from the registrar (2,000 randomly selected from UM-Ann Arbor, and 500 from UM-Flint, which reflects the full annual enrollment of first-year undergraduate students at the UM-Flint campus) and invite them to participate in an 8-minute survey screen of their mental health, with an online consent form. We anticipate approximately 425 students will consent to participate and complete the **screening survey**, and that 142 students will meet criteria for a positive screen of mild-moderate depressive symptoms (PHQ-9 score of 5-14) and no current psychotherapy for the intervention portion of the study. We anticipate that 85% of the 142 participants who screened eligible for the study will continue to this next phase of the study, provide a cell-phone numbers, and complete the **baseline survey** (all within the same Qualtrics flow of the screening survey). The screening survey will be administered to all invited participants who consent to participate and takes approximately 8 minutes to complete. It will be sent out on a Tuesday, with reminders on Friday, and following Monday. Participants are deemed eligible if they score 5-14 on the PHQ-9, denoting mild-to-moderate depressive symptoms **and** report they are not currently enrolled in a form of mental health care (e.g., therapy). The baseline survey will be administered to participants screening positive on the screen, when they provide their cell phone number, and takes 10-15 additional minutes to complete. Randomization (3:1 to intervention versus assessment-only) occurs after baseline survey has been completed. Daily surveys will be administered to participants in the intervention group only, and take approximately 1 minute to complete, with links to the survey texted at 8pm each day. Weekly surveys are administered to all participants on Sunday evenings and take approximately ten minutes to complete. The final follow-up survey takes approximately 25 minutes to complete and will be administered to all randomized participants (n=120) on their sixth Sunday of the project. Administration of all surveys will be conducted via an online, automated system (Qualtrics).

[figure not shown]

Figure 1. Enrollment Flowchart

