#### 10.1.8 QUALITY ASSURANCE AND QUALITY CONTROL

An emphasis will be placed on maintaining strict patient confidentiality. No participant names will be associated with the data. Forms containing identifying information will be kept separate from participant study data and electronic files will be password protected on secured servers. The study platform is HIPAA compliant and will use a secure SMS service (Twilio) to deliver text messages to participants. When data from Qualtrics is downloaded by investigators, the aggregated dataset will contain no PII. Quality control and reliability of assessments will be monitored by the PI, [name]. He will meet weekly with research assistants on the project to monitor the quality of the data files and identify any inconsistencies that may require adjustment to the programming of the Qualtrics survey or study platform.

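### The weekly completeness review of the adverse event log is tied to a recruitment period of about 10 days, so most of the six-week participation falls outside it

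*Combined protocol and SAP*

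**What the plan says.** Section 8.3.4 describes how adverse events are captured, assessed and logged. Its last sentence says of the log that "the log will be additionally reviewed for completeness at weekly intervals during the active recruitment period". No other period is given for this review.

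Two other rules in the same section carry no recruitment limit. On documentation: "All AEs occurring while on study will be documented appropriately regardless of relationship". On escalation: "Within 48 business hours of learning of these events, the coordinator will then bring all possible AEs to the attention of the PI".

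Recruitment is short. Section 5.5 states: "Our full sample will be recruited in this ~10-day period". Section 5.4 gives a slightly longer figure: "the initial screening period for this intervention will occur over the course of only two weeks". Section 8.1 describes one mailing of the screening survey: "It will be sent out on a Tuesday, with reminders on Friday, and following Monday". Participation is much longer. Section 4.1 states: "The total time for study completion for an individual participant is 6 weeks".

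**The concern.** A log review tied to recruitment suits a trial with rolling entry, where recruitment and follow-up largely overlap. Here everyone enters in one brief wave and then takes part for six weeks. The review would stop at about the point where the weekly surveys, feedback reports and text messages are getting under way.

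Section 8.3.1 names worsening depressive symptoms and onset of suicidal ideation as the expected adverse events. The repeated measures of these (the weekly PHQ-9 and the suicidal-thought items) fall mostly after recruitment has closed. Entries made then, including severity, relatedness and date of resolution, would have no scheduled weekly check for completeness. What is at stake is mainly whether the trial's safety record is complete when it is summarised.

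**Working it through.** The plan states no figure for this review's coverage, so there is none to reproduce. The check is timeline arithmetic.

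**Inputs**
- Recruitment length R: 10 days (section 5.5), with 14 days (section 5.4) as the alternative.
- Participation P: 6 weeks = 42 days (section 4.1; section 1.3 also lists 42 daily surveys).
- Review frequency: weekly (section 8.3.4).
- Assumption: entry is spread uniformly over R.

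**Coverage when the six-week clock starts at entry**

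| Quantity | Formula | R = 10 | R = 14 |
|---|---|---|---|
| Weekly reviews inside recruitment | floor(R/7) | 1 | 2 |
| Largest share of one participant's time covered (first enrollee) | R/P | 10/42 = 24% | 14/42 = 33% |
| Mean share covered, uniform entry | (R/2)/P | 5/42 = 12% | 7/42 = 17% |
| First entry to last follow-up | R + P | 52 days = 7.4 weeks | 56 days = 8.0 weeks |
| Share of that span covered | R/(R + P) | 10/52 = 19% | 14/56 = 25% |

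**Coverage when week 1 starts on the Monday after baseline**

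This start is inferred. Section 6.1.1 sends feedback on Mondays, based on the baseline survey in the first week and on the weekly survey in the next five. That implies six Monday-to-Sunday weeks, but no start rule is stated. Take the Tuesday mailing as day 0.
- Earliest enrollee: starts Monday, day 6; first Sunday survey on day 6 + 6 = 12; sixth Sunday on day 12 + 35 = 47.
- Enrolled on day 10 (Friday): starts day 13; sixth Sunday on day 13 + 6 + 35 = 54, or 54/7 = 7.7 weeks after the mailing.
- Enrolled on day 14 (Tuesday): starts day 20; sixth Sunday on day 20 + 6 + 35 = 61, or 61/7 = 8.7 weeks.

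On this clock, no on-trial Sunday survey falls inside a 10-day recruitment period, because the first is on day 12. Under 14 days only the day-12 survey does, since the next is on day 19.

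**Both clocks together.** With 10-day recruitment there is 1 review in 7.4 to 7.7 weeks. With 14-day recruitment there are 2 reviews in 8.0 to 8.7 weeks.

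**With the review extended to the last follow-up.** floor(52/7) = floor(54/7) = 7 reviews for R = 10, and floor(56/7) = floor(61/7) = 8 for R = 14. That is six more than now in either case, or seven with a closing check.

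**The case against.** The strongest reply is that little is lost. The lapsing step is an additional check for completeness. Capture on the case report form, the log, escalation, the investigator's assessment of expectedness and relatedness (section 8.3.4) and reporting to the IRB and NIMH (sections 8.3.5 and 8.3.6) have no recruitment limit. Automated crisis information follows any report of suicidal thoughts in the baseline, weekly or follow-up survey (sections 2.3.3 and 10.1.6), and the log review does not affect it. This stands. A reader might infer that safety oversight ends with recruitment, or that participants are put at risk. The documents do not support either inference.

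A reader might also infer that nothing else could take the review's place. That is too absolute. Section 10.1.7 provides for monitoring so that reported data are accurate and complete, and for IRB review of adverse events. It mitigates the gap without closing it, because it names neither the log nor a weekly check and its IRB reviews are annual. Nor does the weekly meeting in section 10.1.8 fill the gap: "He will meet weekly with research assistants on the project to monitor the quality of the data files". Its stated subject is data files and survey or platform programming.

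It can further be said that the review may not find missed events. Section 8.3.4 does not say that the log is reconciled with survey responses, section 2.3.3 says staff do not monitor those responses, and section 1.3 schedules adverse event reporting only at baseline and the 6-week follow-up. This also stands: the benefit that can be claimed is completeness of entries, and wider event capture is a separate matter.

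Finally, it is tempting to say that the review always stops before the first on-trial survey. That depends on the inferred Monday start and the 10-day figure. If the first Sunday after enrolment counted, a day-0 enrollee's first survey would be on day 5, inside the window.

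**Conclusion.** The point holds as a mismatch between a stated review window and the period it should serve. Section 8.3.4 requires adverse events to be documented while participants are on study, but schedules the weekly completeness review of the log only for recruitment. Nothing in the public text extends that review.

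The size is about 1 review in roughly 7 to 8 weeks, or 2 in roughly 8 to 9 weeks. On average 83% to 88% of participation time is uncovered. These averages assume uniform entry and a clock that starts at entry; the review counts assume one review per completed week of recruitment. That the review stops with recruitment is inferred from the wording, since no other period is given. The authors may have meant the period of active participation, but staff following the text would still stop early.

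The consequence is a weaker check on the completeness of the safety record. Direct harm to participants is not shown. The change is worth making because it is so cheap.

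**What to change.** In section 8.3.4, replace the recruitment-period wording at the end of the log sentence with: *from the first baseline survey until the last participant has completed the 6-week follow-up or been deemed lost to follow-up*. Starting at baseline matches section 1.3, which schedules adverse event reporting there. The end point uses the completion and loss-to-follow-up rules already in sections 4.4 and 7.3.

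The cost is one protocol phrase and about six or seven more short weekly checks of an existing log by existing staff. No eligibility, treatment or analysis rule changes.
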